8 STUDY ENDPOINTS

8.1 Primary Endpoint

- Immunologic efficacy will be assessed by the increase in the total number of tumor-infiltrating CD8+ T cells in the CRC lesions (measured as the ratio between the CD8 mRNA message and the expression of the housekeeping gene HPRT which will be provided by the study statistician in a SAS compatible excel formatted electronic file), and comparing the total number of tumor-infiltrating CD8+ T cells in pre-treatment vs post-treatment biopsies.

8.2 Secondary Endpoints

- Objective response rate by RECIST v1.1
- Overall safety profile characterized by type, frequency, severity (according to CTCAE Version 4.0), timing, seriousness and relationship to study treatment

PROTOCOL TITLE: Phase 2A Study Evaluating a Chemokine-Modulatory Regimen in Patients with Colorectal Cancer Metastatic to the Liver

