2.5 Rationale and significance

As detailed above, a previously-demonstrated correlation between the density of CRC-infiltrating effector T cells and long-term outcomes [11, 12] has been established. In our preclinical ex vivo studies performed using explants of resected metastatic CRC, the combination of IFN α with nonselective or COX2-selective inhibitors of prostaglandin synthesis resulted in elevated production of the effector T cell-attracting chemokines CXCL10 and CCL5. This was associated with concomitant suppression of the intratumoral expression of CCL22, a T_{reg}-attracting chemokine [63, 64]. However, in a subset of patients, the optimal results, particularly with regard to CCL5 induction, required additional stimulation by a third agent, a TLR3 Ligand. NCT01545141 demonstrated the safety of the CKM regimen administered over 5 days, without the emergence of new adverse effects or with compromise of surgical outcomes. However, the brief course, limited patient numbers, and lack of pre-treatment biopsies did not allow for an objective estimate of clinical efficacy nor did it allow for a robust evaluation of the impact of this CKM regimen on the tumor microenvironment. If solid evidence of a beneficial biologic effect on colorectal were demonstrated, this would strongly support further investigation, as a self-standing treatment in adjuvant settings or in combination with checkpoint blockade, vaccination or adoptive T cell transfer, which all depend on the presence of T cells in tumor microenvironments (or the ability of T cells to enter tumors).

We seek to establish the immunologic impact of an abridged 3 day course of a chemokine regimen, consisting of Interferon Alpha-2b, celecoxib, and rintatolimod, administered in repeated sessions over 3 weeks. A 3 day regimen will be used preferentially over the 5 day regimen due to concerns of chronic toxicity with multiple cycles and also for ease of implementation and participant scheduling. We further seek to evaluate clinical activity and to confirm the observed safety profile with repeated dosing. We hypothesize that the proposed chemokine modulation treatment in recurrent/metastatic CRC patients may increase the density of tumor infiltrating lymphocytes (TILS) and provide anti-cancer benefit.

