17 SAFETY EVALUATION

17.1 Adverse Events

17.1.1 Definition

An adverse event or adverse experience (AE) is any untoward medical occurrence associated with the use of a drug in humans, whether or not considered drug related. Therefore, an AE can be ANY unfavorable and unintended sign (including an abnormal laboratory finding), symptom, or disease temporally associated with the use of a medicinal (investigational) product, whether or not considered related to the medicinal (investigational) product (attribution of ‘unrelated’, ‘unlikely’, ‘possible’, ‘probable’, or ‘definite’).

An AE is considered “unexpected” if it is not listed in the investigator brochure or is not listed at the specificity or severity that has been observed; or if an investigator brochure is not required or available, is not consistent with the risk information described in the general investigational plan in other study-related documents.

- **Diagnosis Versus Signs and Symptoms**

If known, a diagnosis should be recorded on the CRF rather than individual signs and symptoms (e.g., record only liver failure or hepatitis rather than jaundice, asterixis, and elevated transaminases). However, if a constellation of signs and/or symptoms cannot be clinically characterized as a single diagnosis or syndrome at the time of reporting, each individual event should be recorded as an AE or SAE on the CRF. If a diagnosis is subsequently established, it should be reported as follow-up information.

- **Adverse Events Occurring Secondary to Other Events**

In general, AEs occurring secondary to other events (e.g., cascade events or clinical sequelae) should be identified by their primary cause. For example, if severe diarrhea is known to have resulted in dehydration, it is sufficient to record only diarrhea as an AE or SAE on the CRF.

However, clinically significant AEs occurring secondary to an initiating event that are separated in time should be recorded as independent events on the CRF. For example, if a severe gastrointestinal hemorrhage leads to renal failure, both events should be recorded separately on the CRF.

- **Abnormal Laboratory Values**

Only clinically significant laboratory abnormalities that require active management will be recorded as AEs or SAEs on the CRF (e.g., abnormalities that require study drug dose modification, discontinuation of study treatment, more frequent follow-up assessments, further diagnostic investigation, etc.).

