17.2 Grading and Reporting Adverse Events

- **Grading and Relationship to Drug**

The descriptions and grading scales found in the CTEP Version 4 of the NCI Common Terminology Criteria for Adverse Events (CTCAE) will be utilized for AE reporting. CTEP Version 4 of the CTCAE is identified and located at:

http://ctep.cancer.gov/protocolDevelopment/electronic_applications/ctc.htm.

AEs not covered by specific terminology listed should be reported with common medical terminology, and documented according to the grading scales provided in the CTCAE Version 4.

The relationship of event to study drug will be documented by the Investigator as follows:

Unrelated: The event is clearly related to other factors such as the participant’s clinical state, other therapeutic interventions or concomitant drugs administered to the participant.

Unlikely: The event is doubtfully related to investigational agent(s). The event was most likely related to other factors such as the participant’s clinical state, other therapeutic interventions, or concomitant drugs.

Possible: The event follows a reasonable temporal sequence from the time of drug administration, but could have been produced by other factors such as the participant’s clinical state, other therapeutic interventions or concomitant drugs.

Probable: The event follows a reasonable temporal sequence from the time of drug administration, and follows a known response pattern to the study drug. The event cannot be reasonably explained by other factors such as the participant’s clinical state, therapeutic interventions or concomitant drugs.

PROTOCOL TITLE: Phase 2A Study Evaluating a Chemokine-Modulatory Regimen in Patients with Colorectal Cancer Metastatic to the Liver

Definite: The event follows a reasonable temporal sequence from the time of drug administration, follows a known response pattern to the study drug, cannot be reasonably explained by other factors such as the participant's condition, therapeutic interventions or concomitant drugs; AND occurs immediately following study drug administration, improves upon stopping the drug, or reappears on re-exposure.

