- **Reporting Adverse Events:** Routine AEs occurring between the start date of intervention until 30 days after the last intervention, or until the event has resolved, the study participant is lost to follow-up, the start of a new treatment, or until the study investigator assesses the event(s) as stable or irreversible, will be reported. New information will be reported after it is received.

Table 2 Guidelines for Routine Adverse Event Reporting (Regardless of Expectedness)

Attribution	Grade 1	Grade 2	Grade 3	Grade 4
Unrelated			X	X
Unlikely			X	X
Possible	X	X	X	X
Probable	X	X	X	X
Definite	X	X	X	X

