It is anticipated that 15 patients will be enrolled to this study. The table above presents the minimum number of subjects experiencing treatment-related SAEs (i.e., those SAEs judged to be possibly, probably, or definitely related to the study regimen) that would dictate suspension of the trial in accordance with the stopping rule. Using these assumptions the trial will be suspended if:

- 2 subjects experience treatment related SAE among the first 2 subjects enrolled
- 3 subjects experience treatment related SAE among 3 – 5 subjects or,
- 4 subjects experience treatment related SAE among 6 – 7 subjects or,
- 5 subjects experience treatment related SAE among 8 – 10 subjects or,
- 6 subjects experience treatment related SAE among 11 – 12 subjects,
- 7 subjects experience treatment related SAE among 13 – 15 subjects.
- Any death not clearly due to the underlying disease or extraneous causes

At the completion of the study, all AEs will be summarized by weekly treatments and grade using frequencies and relative frequencies.

Treatment Related SAEs for Safety Monitoring

Treatment Related SAEs will be defined as the following events that occur during the period of Day 1 through the End of Treatment visit:

- \geq Grade 3 treatment-related non-hematologic toxicities, except:
 - The following grade \geq 3 toxicities (lasting <7 days)
Flu-like symptoms/constitutional symptoms (i.e., fever, chills, arthralgias, myalgias)
Depression, anxiety, restlessness, or insomnia
GI symptoms (i.e., nausea, diarrhea)
AST/ALT (unless accompanied by Grade 2 increased bilirubin)
 - Please note, if the above grade 3 toxicities last ≥ 7 days, they will be defined as a DLT
- \geq Grade 4 treatment related non-hematologic toxicity
- Hy's law criteria:

PROTOCOL TITLE: Phase 2A Study Evaluating a Chemokine-Modulatory Regimen in Patients with Colorectal Cancer Metastatic to the Liver

- An elevated alanine transaminase (ALT) or aspartate transaminase (AST) lab value that is greater than or equal to three times (3X) the upper limit of normal (ULN) and
- An elevated total bilirubin lab value that is greater than or equal to two times (2X) ULN and, at the same time, an alkaline phosphatase (ALP) lab value that is less than 2X ULN,
- As a result of within-protocol-specific testing or, unscheduled testing

Safety Review and Study Suspension

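### The Section 17.2 reporting table filters non-serious grade 1–2 AEs by investigator attribution, although Sections 8.2 and 19.4 set out to describe AE frequency without that restriction

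*Combined protocol and SAP*

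**What the plan says.** Section 8.2 gives the secondary safety endpoint as "Overall safety profile characterized by type, frequency, severity (according to CTCAE Version 4.0), timing, seriousness and relationship to study treatment". It does not confine the endpoint to treatment-related events. Section 17.1.1 defines an adverse event as "any untoward medical occurrence associated with the use of a drug in humans, whether or not considered drug related". Section 19.4 describes the final analysis in one sentence: "At the completion of the study, all AEs will be summarized by weekly treatments and grade using frequencies and relative frequencies".

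Section 17.2 covers attribution and reporting. On attribution it says "The relationship of event to study drug will be documented by the Investigator as follows", and then defines five levels: unrelated, unlikely, possible, probable and definite. The reporting period covers "Routine AEs occurring between the start date of intervention until 30 days after the last intervention", or runs until one of several other end points. The table that follows, whose title opens "Guidelines for Routine Adverse Event Reporting (Regardless of Expectedness", crosses the five levels with grades 1 to 4. Possible, probable and definite events are marked at all four grades. Unrelated and unlikely events are marked at grades 3 and 4 only.

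Section 17.3 separately requires all new SAEs in its window to be reported, with no condition on attribution.

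**The concern.** The endpoint and the planned summary cover AEs in general, but the only table saying which routine events must be reported removes some of them according to the investigator's opinion of cause. If sites follow the table, the output labelled as covering all AEs would, at grades 1 and 2, hold only related events apart from SAEs.

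Three features of this trial make that matter. First, it is single-arm in advanced cancer. Fatigue, fever, nausea and loss of appetite appear among the drug effects in Sections 13.2 and 13.3, yet they can also be put down to the disease, and no control group can show whether the attribution was right. Second, Section 2.5 gives one aim as "to confirm the observed safety profile with repeated dosing", and Section 19.4 notes that the previous Phase I study gave only one cycle, so the description of tolerability depends on this dataset. Third, the definitions of probable and definite in 17.2 both require a known response pattern. A toxicity that is new with this schedule can therefore be rated no higher than possible. One step lower, at grade 1 or 2 and non-serious, it need not be reported.

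**Working it through.** The plan gives no figure to reproduce, so the check sets the rules side by side.

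**1. The reporting table in 17.2, cell by cell**

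| Attribution | Gr 1 | Gr 2 | Gr 3 | Gr 4 |
|---|---|---|---|---|
| Unrelated | – | – | X | X |
| Unlikely | – | – | X | X |
| Possible | X | X | X | X |
| Probable | X | X | X | X |
| Definite | X | X | X | X |

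There are 5 × 4 = 20 cells, of which 16 are marked and 4 are blank. At grades 3–4 all 10 cells are marked. At grades 1–2, 6 of 10 are marked, and all 6 lie in the three related rows.

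**2. One event followed through the plan**

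Take a non-serious grade 2 event rated unlikely.
- Under 17.1.1 it is an AE.
- It falls within the frequency and relationship parts of the endpoint in 8.2.
- It belongs in the summary in 19.4.
- It is not an SAE, so 17.3 does not bring it in.
- Section 12.1 requires a final status on the eCRF only for AEs that lead to discontinuation.
- In 17.2 it falls in a blank cell.

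No section expressly says that it is nevertheless captured for analysis.

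**3. Consequence at grades 1–2**

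Among non-serious grade 1–2 events that must be reported, the related share is 100% whatever the truth. Possible, probable and definite can still be told apart. The split between related and not related cannot be estimated.

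**4. What is outside the effect**

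- Grade 3–4 events: every cell is marked.
- SAEs in the window: reported under 17.3 whatever the attribution.
- The Bayesian stopping rule in 19.4: it counts SAEs rated possibly, probably or definitely related, and those three rows are marked at every grade.

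**5. Size, on assumptions only**

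The documents give neither low-grade event rates nor an attribution split.

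*Events.* If a share s of non-serious grade 1–2 events is rated unrelated or unlikely, reported count = (1 − s) × true count. With s = 0.10, 0.30 and 0.50 the table shows 90%, 70% and 50% of the true count.

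*Patients.* The event share cannot be applied to a proportion of patients, because a patient with several episodes is still counted if any one of them is rated possible or higher. The relevant number is k, the patients whose every episode is rated unrelated or unlikely. With 15 patients, of whom 9 are assumed to have the symptom, reported incidence = (9 − k)/15:

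| k | Reported | Incidence |
|---|---|---|
| 0 | 9/15 | 60% |
| 1 | 8/15 | 53% |
| 3 | 6/15 | 40% |
| 5 | 4/15 | 27% |

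The error can only be downward. Its size could not be recovered from a database built on the table.

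**The case against.** The strongest reply is that the table governs reporting, not data capture. Its title presents it as reporting guidelines. Recording is dealt with elsewhere and without an attribution filter: Section 17.1.1 says what goes on the CRF, Section 17.2 has the investigator document relationship on all five levels with no grade limit, and Section 11.1 and Appendix F list AE recording on every treatment day, at the Day 20 biopsy and at the end-of-treatment visit. On that reading the summary in 19.4 covers all recorded AEs and nothing is lost. This stands as a plausible account of the intention. It does not remove the conflict, because no section says that the table is limited to onward reporting, and staff could reasonably follow it when deciding what to enter.

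A second reply is that possible is a low bar. It asks for a reasonable temporal sequence and allows that other factors could have produced the event. With nine dosing days between Day 1 and Day 17, many of the symptoms named above would qualify and be reported at any grade. This also stands, and it suggests that the loss may be modest. It does not show that the loss is nil, since the definition of unlikely points to the participant's clinical state as the alternative cause.

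A third reply is that the primary endpoint is not touched and that the illustrative percentages rest on no figure in the documents. Both are correct.

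**Conclusion.** The point holds in a limited and conditional form. If the 17.2 table determines what reaches the database, the frequencies of non-serious grade 1–2 AEs in the 19.4 summary are understated by an unknown amount, and the related share at those grades is fixed at 100%. The condition is neither confirmed nor excluded by the text. This is a conflict between rules, and it is cheap to settle.

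A reader might infer more, and the documents do not support it:
- That attribution decides the AE counts as a whole. It does not: grade 3–4 events and SAEs in the window are reported regardless.
- That safety stopping is weakened. The rule counts only related events by design, and the table requires all of them.
- That relationship cannot be assessed at all at low grade. The three related levels remain distinguishable.
- That the study was set up specifically to detect accumulating low-grade toxicity. Section 2.5 speaks of the safety profile with repeated dosing and Section 19.4 of new AEs or SAEs; neither singles out low grades.
- That a particular loss, such as 60% falling to 40%, is expected. That figure is an assumption chosen to show the mechanism.

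**What to change.** In Section 17.2, state that all AEs of any grade and any attribution, from the start of intervention to 30 days after the last intervention, are recorded on the eCRF and analysed. Then either mark the four blank cells (unrelated and unlikely, grades 1 and 2) or say that the table governs onward reporting only. Filling the cells without that statement would widen reporting but leave open what is analysed. The rules in 17.1.1 on laboratory values and pre-existing conditions can stay as they are, since they do not depend on attribution.

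In Section 19.4, tabulate all-cause and treatment-related frequencies by grade and treatment week.

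If the filter is intended, the alternative is to narrow 8.2 and 19.4 to related grade 1–2 events plus all events of grade 3 or higher. That makes the label accurate but gives up the all-cause low-grade description.

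The cost of the preferred change is additional AE entries for about 15 patients, each up to about Day 47 when treatment is not delayed (last dose Day 17 + 30 days). No new visits or procedures are needed.

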8.3 Exploratory Endpoints

- Median progression free survival by RECIST v1.1
- Median overall survival

9 DESIGN

9.1 Study Design

The intratumoral efficacy of the combination of Interferon Alpha-2b, rintatolimod, and celecoxib will be evaluated by administering fixed doses of each drug. Subjects will receive 3 weeks of the Chemokine Modulation (CKM) regimen, administered on days 1, 2, 3, 8, 9, 10, 15, 16, and 17 of protocol treatment, according to the safe established dosing levels (see Table 1). During this time, subjects will be monitored continuously for safety, based on Bayesian analysis.

Table 1 Dosing

[figure not shown]
Components of the chemokine modulation regimen		
Interferon Alpha-2b (20 million units/M ²) IV over 20 minutes once a day for 3 consecutive days, repeated weekly over 3 weeks (days 1,2,3,8,9,10,15,16,17).	Rintatolimod (200 mg) IV once a day for 3 consecutive days, repeated weekly over 3 weeks (days 1,2,3,8,9,10,15,16,17). Initial administration should begin at a slow rate of infusion (approximately 20 cc/ hour). Increase rate to 40cc/hour after 30 minutes.	Celecoxib (200 mg, orally, twice a day) for 3 consecutive days, repeated weekly over 3 weeks (days 1,2,3,8,9,10,15,16,17). Doses should be given approximately 12 hours apart.

PROTOCOL TITLE: Phase 2A Study Evaluating a Chemokine-Modulatory Regimen in Patients with Colorectal Cancer Metastatic to the Liver

9.2 Treatment Phase

A total of three weeks of therapy will be planned. Serial liver biopsies will be obtained, with the first performed prior to initiating therapy and the second performed on Day 20 (\pm 2 days). Following completion of the 3 consecutive weeks of treatment, the study treatment period will conclude. In order to secondarily assess clinical benefit, repeat CT imaging will be assessed at day 46 (\pm 3 days). If a patient completes therapy and a decision is made to pursue a further alternate treatment, the subject will come off study; however, in this circumstance, assessment of the next clinical staging study will be requested for determination of RECIST parameters.

Schema

